In January 2018, the new recommendations and funding for PCV13 that were approved in the Community of Madrid, confirmed that all adults over 60 years of age not previously vaccinated either with PPV23 or PCV13, should receive one dose of PCV13 and those over 18 years with a chronic disease such as Chronic Obstructive Pulmonary Disease (COPD), diabetes, heart failure, regardless of previous vaccination status, should receive one dose of PCV13. Sequential immunisation with both vaccines (PCV13+PPV23) was recommended for adults with high risk immunocompromising conditions.¹¹ This recommendation was based on the burden of non- bacteraemic CAP in adults and the assumption based on the CAPA study (*Epidemiological study assessing the burden of hospitalised CAP due to Streptococcus pneumoniae in adults in Spain using UAD testing*) that there is still a significant burden due to PCV13 serotypes among all hospitalised CAP in adults 18 years and older (9%).¹ As of September 2019,

around 8% of adults 60 years and older have been vaccinated with PCV13 (Table 3), this proportion is expected to increase in the following months/years.

The Regional Health System operates a database known as SISPAL which includes information on previous vaccination history, including influenza, PPV23 and PCV13 vaccination with lot number and date of administration per person. Pneumococcal vaccination status will be based on whether receipt of ≥ 1 dose of PCV13 or PPV23 could be confirmed by electronic registries. We will obtain previous influenza vaccination status (within the last year) via electronic registries as well.

The aim of this study is to evaluate the PCV13 VE against hospitalised VT-pneumococcal CAP among adults aged ≥ 60 years in the Community of Madrid (total population as of January 2018) of 6,578,079 inhabitants, of which 1,511,750 were aged 60 years and older).¹²

Rationale for the addition of Respiratory Syncytial Virus (RSV) testing

Respiratory syncytial virus has long been recognized as a problematic respiratory pathogen causing illness in children^{13, 14, 15} but the scope and impact of RSV in adults is less well-

PFIZER CONFIDENTIAL CT45-GSOP-RF152.0 Low-Interventional Study Protocol Template 05-Dec-2019 Page 20 of 70

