 - Chronic Kidney Disease.
 - Diabetes (with or without complications).
 - Liver Disease.
 - Immunosuppressant Drug Therapy.
 - Autoimmune Disorders.
 - Immunodeficiency.
 - Human Immunodeficiency Virus (HIV).
 - Acquired Immunodeficiency Syndrome (AIDS).
 - Cancer/Malignancy, Solid Tumor only.
 - Cancer/Malignancy, Hematologic only.
 - Organ Transplantation.
 - Cerebrovascular accident (Stroke).
- Number of previous pneumonia events in year prior to admission. PFIZER CONFIDENTIAL CT45-GSOP-RF152.0 Low-Interventional Study Protocol Template 05-Dec-2019 Page 38 of 70

- Healthcare facility exposure in past 3 months, includes inpatients stays, dialysis centers or long-term care, skilled-nursing, assisted-living, rehabilitation, or other healthcare facilities.
- Antibiotic treatment within 14 days prior to admission.

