12.1.3. Analysis Populations

12.1.3.1. Vaccine Effectiveness CAP Population (Primary Analysis Population)

The Primary Analysis Population will include all participants who:

- 1. Meet all inclusion and exclusion criteria.
- 2. Have a final diagnosis consistent with CAP (CAP-Radiologically Confirmed; CAP-Not Radiologically Confirmed or CAP-no chest radiology done).
- 3. Meet the definition of either case or test-negative control from Section 12.1.1.
- 4. Have \geq 5 combined years of pneumococcal vaccination history available.
- 5. Did not receive any pneumococcal vaccination ≤30 days prior to urine sample collection.
- 6. Have not received PCV20 if available in surveillance region during study.

This population will be analysed overall and restricted to immunocompetent subjects which will be all subjects not noted to the immunocompromised in Table 7.

Table 7.Categorization of Risk Factors by Immunocompetence³

Risk factor	Spain's Categorization		
Age	60 +		
Diabetes mellitus	immunocompetent		
Alcoholism	immunocompetent		
Chronic heart disease	immunocompetent		
Chronic liver disease	immunocompetent		
Chronic lung disease	immunocompetent		
Smoking	immunocompetent		
Congenital or acquired asplenia	immunocompromised		
Cerebrospinal fluid leak	immunocompetent		
Cochlear implant	immunocompetent		
Congenital or acquired immunodeficiencies	immunocompromised		
HIV infection	immunocompromised		
Chronic renal failure	immunocompromised		
Nephrotic syndrome	immunocompromised		
Leukemia	immunocompromised		
Hodgkin's disease	immunocompromised		
Lymphoma	immunocompromised		
Generalize malignancy	immunocompromised		
Iatrogenic immunosuppression	immunocompromised		
Solid organ transplant	immunocompromised		
Multiple myeloma	immunocompromised		
Antineoplastic chemotherapy	not specified		
Occupational risk with exposure to metal fumes	not specified		
Bone marrow transplantation	immunocompromised		
Neurologic diseases (eg, cerebral palsy and seizures)	not specified		
Prior IPD	immunocompetent		

These populations will serve as the primary analysis population for the primary endpoint and the secondary objective of calculating VE for PPV23.

³ Official Regional Immunisation Programme in the Community of Madrid, 2019.

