#### At-risk (immunocompetent)

A participant does not fall in the high-risk category, but having any one of the following medical conditions:

- Alcoholism
- Asthma
- Celiac Disease
- Chronic Liver Disease with Hepatic Failure
- Chronic Liver Disease without Hepatic Failure
- Chronic Neurologic Diseases
- Chronic Obstructive Pulmonary Disease
- Coagulation factor replacement therapy
- Cochlear Implant
- Congestive Heart Failure

DMB02-GSOP-RF02 5.0 Statistical Analysis Plan Template 05-Dec-2019
PFIZER CONFIDENTIAL
Page 49
TMF Doc ID: 98.03

- Coronary Artery Disease (CAD)
- CSF Leak
- Diabetes Treated with Medication
- Down syndrome
- Living in a nursing home
- Living in a long-term care facility
- Occupational risk with exposure to metal fumes
- Other Chronic Heart Disease
- Other Chronic Lung Disease
- Other pneumococcal disease risk factors
- Previous Invasive Pneumococcal Disease
- Tobacco smoking (Tobacco/E-Cigarettes)

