## Low-risk (immunocompetent)

If a participant does not fall in high or at-risk category, then the participant will be classified in the low-risk category. These participants will also be treated as immunocompetent.

Risk factor	Spain's Categorization (Protocol Table 7)	eCRF capture	Characterization for SAP
Age	60 +	DOB and symptom onset date	At risk/ immunocompetent
Alcoholism	immunocompetent	Alcoholism	At risk/ immunocompetent
Chronic heart disease	immunocompetent	Congestive heart or failure or coronary artery disease (cad)/ Other chronic heart disease	At risk/ immunocompetent
Chronic liver disease	immunocompetent	Chronic liver disease without hepatic failure/ Chronic liver disease with hepatic failure	At risk/ immunocompetent

ou:			
Chronic lung disease	immunocompetent	Chronic obstructive pulmonary disease/	At risk/
		Asthma/	immunocompetent
		Other chronic lung disease	
Congenital or acquired	immunocompromised	Asplenia	High-risk/
asplenia			immunocompromised
Cerebrospinal fluid leak	immunocompetent	CSF Leak	At risk/
			immunocompetent
Cochlear implant	immunocompetent	Cochlear implant	At risk/
			immunocompetent
Congenital or acquired immunodeficiencies	immunocompromised	Immunodeficiency	High-risk/
	immunocompotent	Dishates treated with mediantian (not	immunocompromised At risk/
Diabetes mellitus	immunocompetent	Diabetes treated with medication (not include diet controlled)	immunocompetent
Generalize malignancy	immunocompromised	,	High-risk/
Ochcianze manghaney	minunocompromiscu	Cancer/manghancy, some tumor	immunocompromised
HIV infection	immunocompromised	Human immunodeficiency virus (HIV)	High-risk/
		- AIDS/	immunocompromised
		Human immunodeficiency virus (HIV)	
Chronic renal failure	immunocompromised	Chronic kidney disease	High-risk/
Nephrotic syndrome			immunocompromise
Leukemia	immunocompromised	Cancer/malignancy, hematologic	High-risk/
Hodgkin's disease	_		immunocompromise
Lymphoma			đ
Multiple myeloma			
Iatrogenic	immunocompromised	Immunosuppressant drug therapy	High-risk/
immunosuppression			immunocompromised
Antineoplastic	not specified		
chemotherapy			
Solid organ transplant	immunocompromised	Organ transplantation	High-risk/
Bone marrow			immunocompromised
transplantation			
Occupational risk	not specified	Occupational risk with exposure to	At risk/
with exposure to metal fumes		metal fumes	immunocompetent
	not enecified	Chronic nauralogie diseases	At risk/
Neurologic diseases	not specified	Chronic neurologic diseases	immunocompetent

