(eg, cerebral palsy and seizures)			minunocompetent
	:	Diii	A4 =:=1=/
Prior IPD	immunocompetent	Previous invasive pneumococcal disease	At risk/
0 1:			immunocompetent
Smoking	immunocompetent	Smoking or e-cigarettes current on	At risk/
		substance abuse CRF	immunocompetent

DMB02-GSOP-RF02 5.0 Statistical Analysis Plan Template 05-Dec-2019 PFIZER CONFIDENTIAL Page 51 TMF Doc ID: 98.03 Items in Madrid column of risk classification grid but not in the Table 7 of the Protocol:

Risk factor	Spain's Categorization	eCRF capture	Characterization in SAP
Down syndrome	not specified	Down Syndrome	At risk/ immunocompetent
Celiac disease	not specified	Celiac disease	At risk/ immunocompetent
Cerebrovascular accident (Stroke)	not specified	Chronic neurologic diseases (specified to include this in CCG)	At risk/ immunocompetent
Coagulation factor replacement therapy	not specified	Coagulation factor replacement therapy	At risk/ immunocompetent
Institutionalized in nursing home or LTC facility	not specified	Nursing home or long-term care facility for those with disability or dependency on subject characteristics/risk determinants eCRF	At risk/ immunocompetent

Items on CRF that are not risk factors in Spain/Madrid:

Risk factor	Spain's Categorization	eCRF capture	Characterization in SAP
Other metabolic disease	Not present	Other metabolic disease	Not a risk factor
Diabetes that is diet controlled	Not present	Diabetes that is diet controlled	Not a risk factor
Pneumonia	Not present	Pneumonia	Not a risk factor

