# Not classified into any risk category

- Other metabolic disease
- Pneumonia
- Diabetes that is diet controlled

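### The SAP treats diet-controlled diabetes as no risk factor in Spain/Madrid, against the protocol table it cites, so some diabetic participants are coded low-risk instead of at-risk

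*SAP*

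**What the plan says.** **Protocol.** Table 7 (section 12.1.3.1) lists "Diabetes mellitus" as an immunocompetent risk factor, with no condition on treatment. Its footnote gives the source as "Official Regional Immunisation Programme in the Community of Madrid, 2019". Section 7 describes the regional PCV13 recommendation as covering "those over 18 years with a chronic disease such as Chronic Obstructive Pulmonary Disease (COPD), diabetes, heart failure, regardless of previous vaccination status". Section 10.3 collects "Diabetes (with or without complications" as medical history. None of these separates diet-controlled from medicated diabetes.

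**SAP.** The Appendix 2.4 grid has a column for Spain's categorization that names protocol Table 7 as its source. In that grid, diabetes mellitus is captured from "Diabetes treated with medication (not include diet controlled". The at-risk list in the same appendix, and the matching list in section 3.4, carry only "Diabetes Treated with Medication". A further table, headed "Items on CRF that are not risk factors in Spain/Madrid", includes diet-controlled diabetes, records Spain's categorization as not present, and characterizes it as not a risk factor. The list of conditions outside every risk category repeats "Diabetes that is diet controlled". Anyone who is neither high-risk nor at-risk is placed in the low-risk class.

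**The concern.** The SAP attributes to Spain a limit that the cited Table 7 row does not contain. Its own data-entry guidance describes the excluded item as diabetes mellitus controlled without diabetic medication, so the item belongs under the Table 7 row by the SAP's own description. No reason is given for the narrowing, and the SAP version history does not mention it.

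Risk level is used in several places:

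- the at-risk proportion in secondary endpoint 3 (SAP 6.2.3.1);
- risk-stratified summaries (SAP 6.2.1.1, 6.2.2.1, 6.3.5.1, 6.3.6.1, 6.3.9.1);
- the candidate risk covariate in the vaccine effectiveness (VE) model (SAP 6.1.1.1);
- the propensity score (SAP 6.1.1.2), where it enters as 0, 1, 2;
- risk-group incidence (SAP 6.3.4.1).

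The covariate matters in principle. The protocol summary warns of confounding by indication, and Table 1 offers PCV13 after earlier PPV23 to people with underlying disease but not to those aged 60 or over without risk factors. Participants with diet-controlled diabetes fit the indication as the protocol words it, but are grouped with people who lack it.

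**Working it through.** **1. Reproduction.** The documents state no at-risk proportion and no diabetes frequency, so there is no planned figure to reproduce.

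**2. Direction.** At-risk status requires any one of a list of conditions in a participant who is not high-risk. Removing a condition from such a list can only lower the at-risk count or leave it unchanged. Each participant removed goes to low-risk. Those with another listed condition (for example smoking, heart or lung disease, or nursing-home residence) do not move.

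**3. Size of the shift in the at-risk share.** Let *d* be the share of CAP participants with diet-controlled diabetes, and *q* the share of those with no other at-risk and no high-risk condition. Both are assumed. The shift is *d* × *q*. Counts use the 3,063 subjects overall in the base case of Protocol 12.1.2.

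| *d* | *q* | Shift (percentage points) | Participants of 3,063 |
|---|---|---|---|
| 1% | 10% | 0.01 × 0.10 = 0.1 | 3 |
| 5% | 25% | 0.05 × 0.25 = 1.25 | 38 |
| 10% | 50% | 0.10 × 0.50 = 5 | 153 |

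**4. Effect on adjusted VE.** I fitted a logistic model to expected cell counts with a true odds ratio of 0.40, the base-case VE of 60%. Assumptions:

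- 1% to 3% of participants have diet-controlled diabetes only and are merged into low-risk;
- 15% to 20% are truly low-risk;
- PCV13 coverage is 4% to 5% in the truly low-risk and 15% to 18% in the others;
- the odds of vaccine-type pneumonia are 1.2 to 2.0 times higher with a risk condition;
- 36% are high-risk and 9% are vaccine-type, as in Protocol 12.1.2.

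With risk level as a covariate, the adjusted odds ratio is 0.401 to 0.405, so VE is (1 − 0.401) × 100 = 59.9% to (1 − 0.405) × 100 = 59.5%. At the 5-point end of step 3, with the least favourable of these inputs, it is 0.408, or 59.2%.

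**5. What does not change.** At-risk and low-risk participants are both immunocompetent under the SAP. The immunocompetent VE set, case and control status, and the sample size are unaffected.

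**6. Risk-group incidence.** SAP 6.3.4 divides the CAP events attributed to a risk condition by the population with the same condition. If both sides drop diet-controlled diabetes, the aggregate rate rises or falls according to whether CAP incidence in that group is below or above that of the remaining at-risk population. If the external denominator counts all diabetes and the numerator only medicated diabetes, the rate is too low. The plan does not say how the denominator source defines diabetes.

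**The case against.** The strongest defence is that the choice looks deliberate. It appears consistently across the SAP's lists and grid, the eCRF has separate items for the two kinds of diabetes, and Appendix 2.4 refers to a Madrid column of a risk classification grid that is not among the documents. The SAP may modify protocol plans, and only major changes to the primary endpoint or its analysis need an amendment. This stands as a possible explanation. It does not remove the conflict, because the SAP presents the exclusion as Spain's own categorization and not as a modification.

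A second defence is that Table 7 sorts risk factors by immunocompetence and does not define an at-risk class. That is correct. The SAP list is also wider than Table 7: it adds items such as Down syndrome, celiac disease and nursing-home residence. The comparison here is therefore with the SAP's own list plus all diabetes, not with Table 7 as a whole, against which the net share could even be higher.

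The Appendix 2.4 grid also codes age 60 and over as at-risk, which taken literally would empty the low-risk class. The at-risk list omits age and the SAP uses a low-risk level throughout, so the reading used here is the workable one.

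Three stronger inferences are tempting and not supported:

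- **VE is materially biased.** Step 4 of the working shows a change of under one percentage point.
- **At-risk incidence is understated.** Step 6 shows that the direction depends on information not in the plan.
- **The misplaced participants supply a large part of PCV13 recipients in the low-risk class.** With 3% misplaced, 15% truly low-risk and coverage of 18% and 4%, the share is 0.0054 / (0.0054 + 0.0060) = 47%; with 1%, 20%, 15% and 5% it is 0.0015 / (0.0015 + 0.0100) = 13%. The 4% to 5% coverage is assumed and lies below every age row of Protocol Table 2, whose minimum is 7.43%. Those rows cover all risk groups, so they do not settle low-risk coverage, but nothing in the documents supports the lower figure. At 10% the same sums give 0.0054 / 0.0204 = 26% and 0.0015 / 0.0215 = 7%.

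**Conclusion.** The contradiction is real and its consequence for coding is automatic: participants whose only listed condition is diet-controlled diabetes become low-risk. The at-risk proportion in secondary endpoint 3 is lower than, or equal to, what the same list would give with all diabetes included. This follows from the definitions alone. The size rests entirely on assumed frequencies, with 0.1 to 5 percentage points as an illustration only. Risk-stratified tables and the risk covariate carry a small misclassification. This is a minor point that affects descriptive outputs and consistency between the documents, and it does not threaten the primary VE result.

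**What to change.** - In SAP 3.4 and Appendix 2.4 (grid and at-risk list), code both eCRF diabetes items, medicated and diet-controlled, as at-risk (immunocompetent), consistent with protocol Table 7.
- Remove diet-controlled diabetes from the table of items said not to be risk factors in Spain/Madrid and from the list of unclassified conditions. Reconcile the age row of the grid at the same time.
- If the regional grid does limit the indication to medicated diabetes, cite that source, reconcile it with Table 7, and report secondary endpoint 3 and the risk-stratified tables with all diabetes counted as at-risk as a sensitivity analysis.
- In SAP 6.3.4.1, state that numerator and denominator use the same diabetes definition.

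The cost is one line of derivation code and a few lines of SAP text. The eCRF already captures diet-controlled diabetes separately, so no new data are needed.

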# Not classified into any risk category

- Other metabolic disease
- Pneumonia
- Diabetes that is diet controlled

# Relevant Guidance of Selected Past Medical History from CCG:

Medical history	Comments
Chronic Obstructive Pulmonary Disease	Also known as emphysema.
Asthma	
Other Chronic Lung Disease	
Congestive Heart Failure	
Coronary Artery Disease (CAD)	
Other Chronic Heart Disease	
	Diabetes mellitus controlled without use of diabetic
Diabetes That Is Diet Controlled	medication.

DMB02-GSOP-RF02 5.0 Statistical Analysis Plan Template 05-Dec-2019 PFIZER CONFIDENTIAL Page 52 TMF Doc ID: 98.03

	Diabetes mellitus treated with any diabetic medication
Diabetes Treated with Medication	(eg, oral hypoglycemics, insulin, or any others).
Other Metabolic Disease	
	Includes chronic neurologic diseases such as epilepsy,
	cerebral palsies, neuromuscular or cerebrovascular
	disease (such as history of cerebrovascular
Chronic Neurologic Diseases	accident/stroke).
Chronic Liver Disease without Hepatic	
Failure	
Chronic Liver Disease with Hepatic Failure	
	Please check this if the subject has any disease risk
04 - P1 Pi Pi-1 F	factors other than the one listed in pre-medical history terms in this eCRF.
Other Pneumococcal Disease Risk Factors	Includes Chronic Kidney Disease (defined as glomerular
	filtration rate <60 mL/min), End-Stage Renal Disease
	(ESRD), nephrotic syndrome, and patients requiring renal
Chronic Kidney Disease	dialysis.
emone money 2 locale	Congenital or acquired immunodeficiencies, including
Immunodeficiency	complement deficiencies and others.
Human Immunodeficiency Virus (HIV) -	HIV-infected person with AIDS diagnosis or CD4<200
AIDS	cells/µl.
Human Immunodeficiency Virus (HIV) - No AIDS	HIV-infected person who has not met AIDS definition.
AIDS	Includes Lymphomas (Hodgkin's disease and others),
Cancer/Malignancy, Hematologic	and Leukemias.
Cancer/Manghaney, Hematologic	Includes solid tumors and other generalized
Cancer/Malignancy, Solid Tumor	malignancies.
	Include solid organ, bone marrow transplantation, and
Organ Transplantation	hematopoietic stem cell transplantation.
	Any immunosuppressant drug therapy that would have
	reduced immune function prior to pneumonia onset,
	including immunosuppressing antineoplastic drug
	therapy and other chronic treatment with known
	immunosuppressant medications, including the use of
	systemic corticosteroids (equivalent of ≥10 mg/day of prednisone) for >14 days within 30 days prior to
Immunosuppressant Drug Therapy	pneumonia event onset.
minutiosuppressant Drug Therapy	Pneumococcal infection from a normally sterile site such
	as blood, pleural fluid and other normally sterile body
Previous Invasive Pneumococcal Disease	fluids, and internal organ/tissue cultures.
Cochlear Implant	
CSF Leak	
Celiac Disease	Cerebrospinal fluid leak.
	Cerebrospinal fluid leak.
Down Syndrome	Cerebrospinal fluid leak.
Down Syndrome Asplenia	Cerebrospinal fluid leak.   Includes congenital or acquired asplenia.
•	
Asplenia	Includes congenital or acquired asplenia.

DMB02-GSOP-RF02 5.0 Statistical Analysis Plan Template 05-Dec-2019 PFIZER CONFIDENTIAL Page 53 TMF Doc ID: 98.03

Occupational risk with exposure to metal fumes	
Coagulation factor replacement therapy	-
Multiple Myeloma	

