%	12	15%	60%	9%	1:10	170	1692	1862	1960	50%	3920	3.4
enrolled	13	15%	60%	9%	1:10	170	1692	1862	1960	30%	6533	5.7

Table 6.Sample Size Scenarios for VE Calculations At Interim

- a. Base case values are highlighted in gray; 2.5% alpha was used for all scenarios and 80% power was used for all scenarios except #11. All calculations done with OpenEpi, Version 3, open-source calculator (Sample Size-Unmatched Case Control Study; available @ https://www.openepi.com/SampleSize/SSCC.htm) and used Fleiss method with continuity correction, which is consistent with estimates based on Fischer's exact test. For these calculations, 2.5% alpha was used to split alpha allocated between interim analysis and final analysis (ie, 2.5% to each analysis).
- b. Includes projected 5% of subjects with no valid pneumococcal serotype specimen result.
- c. Number of "CAP inpatients needed" is based on the percentage of CAP patients enrolled in prior column, which accounts for loss of potential subjects who declined participation or were not offered participation due to incomplete surveillance.
- d. Estimate 1800 CAP admissions annually in the surveillance area and 36% would be immunocompromised, leaving ~1150 immunocompetent CAP admissions annually and ~104 vaccine-type pneumococcal CAP cases.

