Appendix 2.3. Risk class assignment based on pneumonia severity index

# Appendix 2.4. Risk Classification

#### High risk (immunocompromised)

A participant falls in any of the following medical conditions:

- Asplenia
- Cancer/Malignancy, Hematologic
- Cancer/Malignancy, Solid Tumor
- Chronic Kidney Disease
- Human Immunodeficiency Virus (HIV) AIDS
- Human Immunodeficiency Virus (HIV) No AIDS
- Immunodeficiency
- Immunosuppressant Drug Therapy
- Multiple Myeloma
- Organ Transplantation

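### SAP Appendix 2.4 counts any solid tumour as immunocompromised where protocol Table 7 counts only generalised malignancy, so the immunocompetent VE analysis uses a population the protocol does not define

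*SAP*

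**What the plan says.** The primary objective asks for PCV13 effectiveness overall and in immunocompetent persons. Protocol 12.1.3.1 says the primary population is also analysed "restricted to immunocompetent subjects which will be all subjects not noted to the immunocompromised in Table 7". Table 7, attributed to the regional immunisation programme, marks "Generalize malignancy", "Chronic renal failure", nephrotic syndrome and iatrogenic immunosuppression, among others, as immunocompromised. It lists "Antineoplastic chemotherapy" but leaves its class unspecified.

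SAP Appendix 2.4 prints a crosswalk from Table 7 to eCRF items:

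- Generalised malignancy becomes "Cancer/Malignancy, Solid Tumor". The completion guidance in the same appendix says this item "Includes solid tumors and other generalized" malignancies.
- Chronic renal failure and nephrotic syndrome become chronic kidney disease, which the guidance extends to a glomerular "filtration rate <60 mL/min), End-Stage Renal Disease", nephrotic syndrome and dialysis.
- Immunosuppressing antineoplastic drugs are placed under immunosuppressant drug therapy.

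All three items are high-risk, that is, immunocompromised, and their holders leave the immunocompetent model. SAP 6.1.1.1 also uses immune class in its exclusions from every VE analysis: PCV13 within one year after PPV23 for immunocompetent participants, within eight weeks for immunocompromised ones.

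For sizing, Table 6 footnote d assumes that of 1,800 yearly CAP admissions "36% would be immunocompromised, leaving ~1150 immunocompetent CAP admissions annually".

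**The concern.** The restricted analysis is meant to set aside people who may not respond to the vaccine. A patient with a localised solid tumour and no immunosuppressive treatment belongs in that analysis under Table 7 and is removed from it under the SAP. The two documents therefore define different target populations for half of the primary objective.

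The overall analysis is touched as well. If that patient had received PCV13 six months after PPV23, the SAP's one-year rule would exclude them from all VE analyses under the Table 7 class, while the eight-week rule keeps them under the SAP class.

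Protocol 12.4 and the SAP introduction both say that major changes to the primary endpoint definition or its analysis go into a protocol amendment. Protocol version 3.0 still points to Table 7, and the SAP version history does not mention a wider class.

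**Working it through.** **Side-by-side reading.**

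| Condition | Protocol Table 7 | SAP Appendix 2.4 | Reading |
|---|---|---|---|
| Solid tumour, not generalised | not listed, so immunocompetent | high-risk | SAP is wider |
| Generalised malignancy | immunocompromised | high-risk | agree |
| Chronic renal failure | immunocompromised, no threshold | GFR below 60 and more | SAP may be wider |
| Antineoplastic chemotherapy | not specified | high-risk if immunosuppressing | to be settled |

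Every other Table 7 entry marked immunocompromised (asplenia, immunodeficiency, HIV, haematological malignancy and myeloma, transplantation, iatrogenic immunosuppression) is also high-risk in the SAP. The SAP's immunocompetent set is therefore contained in the protocol's.

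**The plan's own figure.** Inputs for Table 6 scenario 2: coverage in controls p0 = 0.15, VE 60% (OR = 0.4), r = 10 controls per case, two-sided alpha 0.025, power 80%, Fleiss with continuity correction.

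- Odds in cases: 0.4 × 0.15/0.85 = 0.0706, so p1 = 0.0659 and d = p0 − p1 = 0.0841. Pooled p = (0.0659 + 10 × 0.15)/11 = 0.1424.
- Uncorrected n = [2.2414 × √(11 × 0.1424 × 0.8576) + 0.8416 × √(10 × 0.0659 × 0.9341 + 0.15 × 0.85)]² / (10 × 0.0841²) ≈ 156.3, rounded up to 157.
- Corrected n = (156.3/4) × [1 + √(1 + 22/(156.3 × 10 × 0.0841))]² ≈ 169.1, rounded up to **170 cases**, as stated.
- The same method gives 259 cases for VE 50%, also as stated.
- Accrual: 1,862/0.95 = 1,960 enrolled; 1,960/0.70 = 2,800 CAP inpatients; 1,800 × 0.64 = 1,152 immunocompetent admissions a year; 2,800/1,152 = 2.43 years; 1,152 × 0.09 = 103.7 vaccine-type (VT) cases a year. All agree with Table 6.

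**Sensitivity to the immunocompromised share s.** The documents give no share under the SAP definition, so every row below 36% is an assumption. Admissions = 1,800 × (1 − s). Years = 2,800/admissions (170 cases) or 4,275/admissions (259 cases). Evaluable VT cases in 4 years = admissions × 4 × 0.70 × 0.95 × 0.09.

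| s | Admissions/yr | VT cases/yr | Years to 170 | Years to 259 | Evaluable VT cases, 4 yr |
|---|---|---|---|---|---|
| 36% | 1,152 | 103.7 | 2.43 | 3.71 | 276 |
| 46% | 972 | 87.5 | 2.88 | 4.40 | 233 |
| 50% | 900 | 81.0 | 3.11 | 4.75 | 215 |
| 56% | 792 | 71.3 | 3.54 | 5.40 | 190 |

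Break-even shares for 4 years: 1 − (2,800/4)/1,800 = 61% for the 170-case target, and 1 − (4,275/4)/1,800 = 41% for the 259-case target. At two-sided alpha 0.05 the VE 50% scenario needs about 214 cases, which is met at 46% (233) but not at 56% (190).

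**The case against.** The strongest defence is that the SAP follows the data the protocol collects. Protocol 10.3 records solid tumour and chronic kidney disease as single history items and has no item for generalised malignancy or renal failure. The crosswalk is printed openly, and Appendix 2.4 refers to a Madrid risk grid that is not reproduced. This explains the mapping. It does not change the protocol's definition, which points to Table 7 alone. The guidance wording could also be read as treating solid tumours as generalised disease, but it gives sites no criterion of stage or activity.

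Several stronger readings are tempting, and the defence is right to resist them:

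- **That the analysis is smaller than the study was sized for.** The 36% comes from a cited study whose definition is not shown and is never tied to Table 7. If that study counted any solid tumour or kidney disease, the SAP set is the sized set.
- **That a patient with a GFR of 55 is immunocompetent under Table 7.** Table 7 gives no threshold, so GFR below 60 may simply make an undefined term operational.
- **That patients cured years ago are removed.** The guidance is silent on past disease.
- **That confounding control is materially weakened.** Risk level is a candidate covariate and a propensity variable. But protocol Table 1 offers PCV13 to unvaccinated people aged 60 and over in every risk group, and PPV23 in the past 5 years is a separate covariate. The documents support neither a direction nor a size of bias.

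The immunocompetent target is also a case count, so a smaller pool mainly lengthens accrual, and the SAP has dropped the interim VE analysis that the 2.4 years was meant to date.

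**Conclusion.** The tumour mismatch is established from the text. The immunocompetent VE analysis, and the exclusions that depend on immune class, use a different population from the one protocol 12.1.3.1 defines, without an amendment. The renal and antineoplastic entries are to be reconciled. They are not shown contradictions: Table 7 also lists iatrogenic immunosuppression, which may already cover some of those drugs.

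The harm is mainly to what is being estimated. The number of patients reclassified is unknown, and so is the number affected by the interval exclusions, which may be small. No loss against the planned size is demonstrated. If the SAP share were 46% to 56%, the base case would still be reached within 4 years. The VE 50% scenario at alpha 0.025 would not be. Both statements rest on the protocol's 1,800 admissions, 9% VT share, 70% enrolment and 95% valid results.

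**What to change.** 1. Reconcile Table 7 and Appendix 2.4 for solid tumour, kidney disease and antineoplastic treatment, either by amending the protocol or by aligning the SAP mapping. Record the choice in the version history.
2. State which definition of immunocompromised the 36% refers to.
3. Pre-specify the immunocompetent VE twice: as the SAP now defines it, and again with patients whose high-risk items are confined to solid tumour, chronic kidney disease or both counted as immunocompetent. Apply the interval exclusions according to the class used in each run. Apart from the antineoplastic question, the Table 7 population lies between these two sets, so the pair shows how far the definition matters, although the two estimates are not strict bounds.
4. Use discharge codes to refine the split only where they exist. The schedule of activities and protocol 10.5 say only that they may be supplied, and they may not separate localised from generalised disease.

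The second run uses eCRF fields already collected. The cost is the wording changes and one extra analysis.
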